### Power Calculation

Based on data from the study ICUs in the year prior to the trial, we anticipate the planned study duration (Figure 1) will result in enrollment of around 14,000 patients with an overall rate of MAKE30 around 15%. Enrollment of 14,000 patients will provide 90% power at an alpha level of 0.05 to detect an absolute difference between the saline and balanced crystalloid groups in MAKE30 of 1.9%, a relative risk reduction of 12%, which is comparable to the 12% relative risk reduction for in-hospital mortality reported in a recent pilot trial[13] (additional details in the Appendix 3).

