#### **Final Sample Size Justification**

*(Protocol Amendment 5/10/16; Published with Statistical Analysis Plan 3/16/17)*

As a cluster-randomized, multiple-crossover trial, SMART will enroll for a fixed duration to account for seasonal effects and ensure an equal number of study periods in which each study unit is assigned to each study arm. The final planned study duration is 82 unit-months over a calendar period of two years. The total number of patients enrolled will depend on the rate of admissions to study ICUs during the fixed time period of the trial.

Principal Investigators: [name], [name]

Version Date: 6/15/17

Study Title: Isotonic Solutions and Major Adverse Renal Events Trial (SMART)

Institution/Hospital: Vanderbilt University Medical Center

Based on data from the study ICUs in the year prior to the trial, we anticipated that the final planned study duration of 82 unit-months would result in enrollment of around 14,000 patients with an overall rate of MAKE30 around 15%. Enrollment of 14,000 patients would provide 90% power at an alpha level of 0.05 to detect an absolute difference between the saline and balanced crystalloid groups in MAKE30 of 1.9%, a relative risk reduction of 12%. This relative risk reduction is similar to the relative risk reduction reported in prior research comparing balanced crystalloid to saline among critically ill adults.

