### **Final Anticipated Sample Size**

*(Protocol Amendment 3/29/17)*

As a cluster-randomized, multiple-crossover trial, SMART will enroll for a fixed duration, 82 unit-months over a calendar period of two years, and the total number of patients enrolled will depend on the rates of admissions to study ICUs during the fixed time period of the trial. The number of patients admitted to each of the participating ICUs has increased over the duration of the trial and we now anticipate at least 15,000 and no more than 16,500 patients will be enrolled during the planned study period.

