### Study Sites and Period

SMART is being conducted in five academic ICUs at Vanderbilt University Medical Center: a 34-bed medical ICU, a 22-bed neurological and neurosurgical ICU, a 27-bed cardiovascular ICU, a 31-bed trauma ICU, and a 22-bed surgical ICU. Participating ICUs began enrollment sequentially over the first year of the study (Figure 1). Each ICU will enroll patients for at least 12 months and will enroll for an equal number of saline and balanced crystalloid months.

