## Primary Analysis

To account for the cluster-level-allocation, cluster-level-crossover structure of the trial, the primary analysis will be an intention-to-treat comparison of the primary outcome of MAKE30 between the saline and balanced crystalloid groups using a generalized linear mixed-effects model including fixed effects (group assignment, age, gender, race, source of admission, mechanical ventilation, vasopressor receipt, diagnosis of sepsis, and diagnosis of traumatic brain injury) and random effects (intensive care unit)[27,28].

In preparation for SMART, we electronically collected the same set of variables that would be used to analyze SMART from the records of all 11,582 patients admitted to the study ICUs between January 1, 2014 and December 31, 2014. With the data on MAKE30 from the 11,582 patients admitted in the year before the trial, using generalized linear mixed-effects modeling treating the five ICUs as clusters and the 12 months as periods, we calculated the intra-cluster correlation coefficient to be 0.142, the intra-period correlation coefficient to be 0.026, and the intra-cluster intra-period correlation coefficient to be  $<0.001$ .

Using the data from the 11,582 patients admitted in the year before the trial, we performed a series of simulated trials evaluating a variety of trial conditions and potential results including: (1) outcome differences between groups ranging from no difference to a 50% relative risk reduction, (2) heterogeneity of treatment effect by cluster, (3) change in the incidence of the outcome in the control group over the course of the trial, (4) varying levels of intra-cluster correlation, and (5) varying levels of intra-period correlation. In each case the generalized linear mixed-effect model appeared to adequately account for the correlation between participants. Analysis using generalized linear mixed-effects modeling and generalized estimating equations accounting for the same variables produced identical odds ratios and 95% confidence intervals for the difference between the simulated groups in the primary outcome.

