## DISCUSSION

Upon completion, SMART will provide the most comprehensive data to date on the comparative effects of saline versus balanced crystalloids among critically ill adults. Given that isotonic crystalloid administration represents the most common intervention provided to hospitalized patients, saline and balanced crystalloids are the only available options for isotonic crystalloid administration, and the relationship between saline and acute kidney injury and death remains unclear, the results of SMART will have immediate implications for the care of a broad population of acutely ill patients. Results showing superior clinical outcomes in the balanced crystalloids group would provide compelling evidence that balanced solutions should be considered the preferred isotonic crystalloid for most acutely ill patients. Better clinical outcomes with saline would cement 0.9% sodium chloride as the first line isotonic intravenous fluid and end the current debate about optimal crystalloid composition. In this comparative effectiveness trial of thousands of critically ill adults, a finding of no difference between groups would still have important implications for clinical care and future research. In a trial powered to detect absolute risk reductions as small as 2% in clinical outcomes, no difference between groups would imply that the effect of crystalloid choice for the majority of ICU patients is minimal and any future research would need to focus on select subpopulations.

While designing SMART, we weighed the relative advantages and disadvantages of multiple study designs, including a blinded, patient-level randomized trial. A major challenge to controlled studies of fluid administration in critical illness is the ability to enroll patients prior to the period of highest fluid exposure. As the majority of fluid is administered as part of resuscitation in the emergency department and first 12 hours of ICU admission, we selected a cluster-level-allocation design that would allow enrollment immediately upon presentation and coordination between study ICUs and the emergency department to maximize exposure to the assigned crystalloid and minimize exposure to the non-assigned crystalloid. By basing study group assignment at the unit level, we ensured delivery of the assigned crystalloid even among unstable patients for

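### The 90% power at 14,000 is an independent-patient figure: no allowance is shown for the reported month correlation, which the primary model also omits, and 14,000 does not follow from the 2014 count

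*Combined protocol and SAP*

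**What the plan says.** The SAP's Power Calculation expects around 14,000 patients and an overall MAKE30 rate around 15%, and credits both to data from the study ICUs in the year before the trial. It then says "Enrollment of 14,000 patients will provide 90% power at an alpha level of 0.05 to detect an absolute difference" of 1.9 points, described as a 12% relative reduction. Protocol 12.0 (6/15/17), Final Sample Size Justification, repeats the claim ("Enrollment of 14,000 patients would provide 90% power at an alpha level of 0.05"), as does the power calculation in the published plan. Appendix 3 of the SAP repeats the N and the effect. None of these gives two arm rates, a design effect or a correlation.

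The SAP's Primary Analysis section describes "11,582 patients admitted to the study ICUs between January 1, 2014 and December 31, 2014" as the source for planning. From them it reports an ICU correlation of 0.142, then "the intra-period correlation coefficient to be 0.026, and the intra-cluster intra-period correlation coefficient to be" below 0.001. The covariate list of the primary model ends "diagnosis of traumatic brain injury) and random effects (intensive care unit"; no month term is listed.

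Protocol 12.0, Final Anticipated Sample Size, later says "we now anticipate at least 15,000 and no more than 16,500 patients will be enrolled during the planned study period". It gives no power for that number. The SAP Discussion relies on the power claim when it says how a null result would be read: "In a trial powered to detect absolute risk reductions as small as 2% in clinical outcomes".

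**The concern.** Treatment is assigned by ICU and month, so patients treated in the same month are not independent. The sponsor estimated that dependence from its own data but shows no use of it in the power figure. Because every ICU crosses over, the ICU correlation of 0.142 costs almost nothing. The month correlation does not cancel in the same way. Three ICUs follow one sequence and two the opposite one, with staggered starts, so within a calendar month the two arms hold unequal numbers of patients. If month is left out of the model, month-to-month variation enters the treatment contrast without entering its standard error.

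The Discussion would take a finding of no difference to mean a minimal effect, because of what the trial is powered to detect. That inference needs a power figure, and a type I error, that belong to this design and this model.

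**Working it through.** **Reproducing the 90%.** Two-sided 0.05, n = N/2 per arm: power = Φ(Δ/SE − 1.96), with SE = √{[p₁(1−p₁) + p₂(1−p₂)]/n}.

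- 15% as the saline rate, 15.0% vs 13.1%, n = 7,000: SE = √[(0.1275 + 0.1138)/7,000] = 0.00587; 0.019/0.00587 = 3.236; Φ(1.276) = 89.9%. Relative reduction 1.9/15.0 = 12.7%.
- 15% as the overall rate, 15.95% vs 14.05%: SE = √[(0.1341 + 0.1208)/7,000] = 0.00603; 0.019/0.00603 = 3.149; Φ(1.189) = 88.3%. Relative reduction 1.9/15.95 = 11.9%.

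So the stated power fits the first reading and the stated 12% fits the second. Rounding covers the gap: a difference of 1.85–1.95 points with an overall rate of 14.5–15.5% gives about 86–91%. This is an ambiguity, not an error. Both calculations treat patients as independent.

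**Putting the month correlation in.** The SAP does not state the scale of 0.026. On the logit scale, total variance is (π²/3)/(1 − 0.142 − 0.026 − 0.001) = 3.29/0.831 = 3.96, and month variance is 0.026 × 3.96 = 0.103. Counting only month and residual variance gives 3.29 × 0.026/0.974 = 0.088, which was also tried for the ICU-only model.

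Assumptions: 82 unit-months split 22/18/16/14/12 (medical, neurological, cardiac, trauma, surgical), monthly alternation, the three-versus-two split, and volumes either equal or proportional to beds ("a 34-bed medical ICU, a 22-bed neurological and neurosurgical ICU, a 27-bed cardiovascular ICU, a 31-bed trauma ICU, and a 22-bed surgical ICU"). ICU-month correlation is zero and covariates are left out.

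For the ICU-only model, let V be the ratio of the actual variance of the treatment estimate to the variance the model reports, and δ = Δ/SE from above. Then:

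- type I error = 2Φ(−1.96/√V)
- rejection rate of the nominal test = Φ((δ − 1.96)/√V)
- power at a true 5% level = Φ(δ/√V − 1.96)

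Example at 14,000, equal volumes, 15.0% vs 13.1%, V = 1.47 (√V = 1.212): type I error 2Φ(−1.617) = 10.6%; rejection rate Φ(1.276/1.212) = Φ(1.053) = 85%; power at a true 5% level Φ(3.236/1.212 − 1.96) = Φ(0.71) = 76%.

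Ranges over the assumptions (where two are given: 15.0 vs 13.1, then 15.95 vs 14.05):

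| | N = 14,000 | N = 15,829 |
|---|---|---|
| Independent patients | 89.9%; 88.3% | 93.1%; 91.8% |
| ICU and month modelled | 85–88%; 83–86% | 89–91%; 88–90% |
| ICU only: rejection rate of nominal 5% test | 83–86%; 81–84% | 86–89%; 84–87% |
| ICU only: type I error | about 10–15% | slightly higher |
| ICU only: power at a true 5% level, both pairs | about 65–78% | about 67–82% |

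The third row is not power at alpha 0.05, because the same test rejects a true null two to three times too often. A larger N helps little in the last row, since month variance does not shrink with more patients per month. An ICU-month correlation at its 0.001 ceiling would take the month-modelled figure at 14,000 to 80–85% or 77–83%.

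**Where 14,000 comes from.** The 2014 count covers five ICUs for 12 months, or 60 unit-months.

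- Equal volumes: 11,582/60 × 82 = 15,829.
- Volumes by beds: (34×22 + 22×18 + 27×16 + 31×14 + 22×12)/136 = 2,274/136 = 16.72 months; 11,582 × 16.72/12 = 16,138.
- Needed for 14,000: 14,000/11,582 × 12 = 14.5 volume-weighted months per ICU, against a simple average of 82/5 = 16.4.

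**The case against.** The sponsor can fairly say four things.

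First, the 90% reproduces, so nothing was miscalculated. That stands; the fault is that the figure answers a simpler design.

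Second, the correlations were not ignored. The Primary Analysis section describes simulations from the 2014 patients with varying intra-period correlation and finds the mixed model adequate. The Discussion calls the period effects small, and the published plan refers to a supplementary file for power and model details. This shows that the issue was considered. But the protocol, the SAP and Appendix 3 report no simulated power or type I error, and nothing ties the 90% to those simulations.

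Third, the design-based figures rest on inputs the documents do not fix. ICU volumes are not given for 2014, the correlation scale is not stated, and the SAP's schedule figure shows the medical ICU for 23 months where 22 was assumed. Baseline covariates could raise power. This stands, and is why ranges are given.

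Fourth, 14,000 is too low rather than too high, enrollment is fixed by duration, and the later forecast contains 15,829. This also stands.

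A reader might infer that the trial is too small, or that the primary analysis has been shown to inflate type I error. The documents support neither. Read on the proportion scale, 0.026 with month unmodelled would give about 46–64% at 14,000, but nothing says that scale applies, and the coefficient came from a generalized linear mixed model. With month modelled, the difference detectable with 90% power at a 15% overall rate is 2.03–2.10 points at 14,000 and about 1.9–2.0 at 15,000–16,500, which roughly supports the Discussion's figure.

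**Conclusion.** Wrong as written: the plan states a power that the design is not shown to have. The size depends on the model. With calendar month modelled, the loss from the stated 90% is a few points at 14,000 and is largely recovered at the enrollment now expected, before any ICU-month correlation. With ICU as the only random effect, and the reported month correlation present on the logit scale, the loss is not modest, and it appears as excess type I error as well as lost power. Confidence is medium, because schedule, volumes and correlation scale are assumed. The 14,000 is a separate, conservative inconsistency that the later forecast mostly supersedes. The arm-rate mismatch is rounding.

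**What to change.** Restate the power paragraph in Protocol 12.0 (Final Sample Size Justification), the SAP's Power Calculation and the published plan's power calculation:

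- Give one expected N within 15,000–16,500, consistent with the 2014 count.
- Give both arm rates with a matching absolute and relative effect. On the current wording these are 15.95% vs 14.05%, 1.9 points and 11.9%.
- State the scale of the reported correlations.
- Replace 90% with the power or minimum detectable difference, together with the type I error, from the existing 2014-data simulations. Run them on the actual ICU-by-month schedule, once with the ICU-only model and once with a calendar-month term added.
- Cite the figure for the final primary model beside the Discussion's 2% statement, in both the SAP and the published plan.

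If nothing is rerun, say plainly that 90% assumes independent patients and a 15.0% saline rate.

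The cost is text changes and a rerun of simulations the sponsor already has. The stated power may become less favourable. No extra patients are needed.

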### Data and Safety Monitoring Board and Interim Analysis

A Data and Safety Monitoring Board (DSMB) was appointed to oversee the conduct of the trial and review two interim analyses. The DSMB is comprised of two academic intensivists outside the study institution experienced in the conduct of clinical trials in critical illness. The first interim analysis occurred six months after study initiation, examining patients enrolled between June 1, 2015 and November 30, 2015. The second interim analysis occurred halfway between the first interim analysis and the end of the trial, examining patients enrolled between June 1, 2015 and July 31, 2016 (additional details in the Appendix 4). Both interim analyses used the same stopping criteria: *“The stopping boundary for efficacy will be met if (1) the unadjusted difference in the incidence of the primary outcome (MAKE30) between study groups is greater than or equal to 2.6% with a P value less than 0.001 AND (2) the P value is less than 0.001 for the difference between study groups in the incidence of either in-hospital mortality or receipt of new RRT. As even small differences between groups would be clinically meaningful, and given the importance of determining with as much certainty as possible whether balanced crystalloids are superior to saline, a futility stopping boundary will not be employed. Use of the conservative Haybittle-Peto boundary ( $P <$*

*0.001) will allow the final analysis to be performed using an unchanged level of significance ( $P = 0.05$ ).*” At the time of this submission, both interim analyses have been completed and the DSMB has recommended continuing the trial to completion.

In addition, the DSMB is available to evaluate adverse events or serious adverse events during the conduct of the trial. In cases of serious adverse events, the DSMB has the ability to pause the trial to investigate possible safety issues and suggest changes to the design of the study to abrogate any safety issues.

### **Statistical Analysis Principles**

All analyses will be performed using R version 3.2.0 (R Foundation for Statistical Computing, Vienna, Austria). To maximize transparency and reproducibility, a complete version of the R code that will be used to analyze the final study data is available in Additional File 1. This ensures that (1) statistical reviewers or external investigators will be able to replicate the pre-specified analysis of the trial independently and (2) any changes or additions to the statistical analysis introduced by investigators or reviewers after completion of enrollment will be evident as differences between the pre-specified code and the analysis code included with the final publication.

All analyses will be conducted at the level of the individual patient during an individual hospitalization in an intention-to-treat fashion unless otherwise specified. Continuous variables will be reported as mean  $\pm$  standard deviation, mean and 95% confidence interval, or median and interquartile range; categorical variables as frequencies and proportions. Between-group comparisons will be made with the Mann-Whitney rank sum test for continuous variables, chi-square test for categorical variables, generalized estimating equations for repeatedly measured variables, and generalized linear mixed-effects models for analyses of the primary and secondary outcomes. A two-sided  $P$  value  $< 0.05$  will be considered to be statistically significant.

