## Secondary Outcomes

Secondary outcomes will include additional clinical outcomes, additional renal outcomes, and biochemical outcomes. Additional clinical outcomes will include in-hospital mortality before ICU discharge, before 30 days, and before 60 days; ICU-free days, ventilator-free days, vasopressor-free days, and RRT-free days, all through 28 days after enrollment. Additional renal outcomes will include new RRT receipt, persistent renal dysfunction, stage II or greater AKI by Kidney Disease Improving Global Outcomes (KDIGO) creatinine criteria[26], highest serum creatinine value, change from

baseline creatinine to highest creatinine, final serum creatinine value before hospital discharge, and duration of new RRT. Biochemical outcomes will include serum values for sodium, potassium, chloride, bicarbonate, blood urea nitrogen, and creatinine from enrollment through day 30.

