**Table E4. Serum laboratory values.**

Laboratory value	Saline (n = )	Balanced (n = )	P value
Serum sodium, mmol/L			
Highest between enrollment and day 30, median [IQR]	--	--	--
Lowest between enrollment and day 30, median [IQR]	--	--	--
>145 between enrollment and day 30, No. (%)	--	--	--
< 135 between enrollment and day 30, No. (%)	--	--	--
Serum potassium, mmol/L			
Highest between enrollment and day 30, median [IQR]	--	--	--
Lowest between enrollment and day 30, median [IQR]	--	--	--
> 5.0 between enrollment and day 30, No. (%)	--	--	--
< 3.0 between enrollment and day 30, No. (%)	--	--	--
Serum chloride, mmol/L			
Highest between enrollment and day 30, median [IQR]	--	--	--
Lowest between enrollment and day 30, median [IQR]	--	--	--
> 110 between enrollment and day 30, No. (%)	--	--	--
< 90 between enrollment and day 30, No. (%)	--	--	--
Serum bicarbonate, mmol/L			
Highest between enrollment and day 30, median [IQR]	--	--	--
Lowest between enrollment and day 30, median [IQR]	--	--	--
> 30 between enrollment and day 30, No. (%)	--	--	--
< 20 between enrollment and day 30, No. (%)	--	--	--

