**Table E5. Indications for new renal replacement therapy.**

Indication, No. (%)	Saline (n = )	Balanced (n = )	P Value
Oliguria	--	--	--
Hyperkalemia with serum potassium > 6.5 mEq/L	--	--	--
Acidemia with pH < 7.20	--	--	--
Blood urea nitrogen > 70 mg/dL	--	--	--
Serum creatinine > 3.39 mg/dL	--	--	--
Organ edema	--	--	--
Other renal failure–related indication	--	--	--
Other non–renal failure–related indication	--	--	--

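### The tests named for the unadjusted P values in Tables E3 and E4 ignore ICU and month, so their false-positive rate may exceed 5%; which test Table E4 uses is unclear.

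*Combined protocol and SAP*

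**What the plan says.** Statistical Analysis Principles in the SAP, repeated in the Final Data Analysis Plan of the 6/15/17 protocol, sets the unit of analysis: "All analyses will be conducted at the level of the individual patient during an individual hospitalization in an intention-to-treat fashion unless otherwise specified". It then assigns tests: "Between-group comparisons will be made with the Mann-Whitney rank sum test for continuous variables, chi-square test for categorical variables". The same sentence goes on: "generalized estimating equations for repeatedly measured variables, and generalized linear mixed-effects models for analyses of the primary and secondary outcomes". A two-sided P below 0.05 "will be considered to be statistically significant".

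Three supplementary tables have a P value column: Table E3 (fluids and blood products), "Table E4. Serum laboratory values" and "Table E5. Indications for new renal replacement therapy". None is marked as adjusted. Table 2, by contrast, has columns for an adjusted odds ratio and an adjusted P value.

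The Secondary Outcomes section bears on Table E4: "Biochemical outcomes will include serum values for sodium, potassium, chloride, bicarbonate, blood urea nitrogen, and creatinine from enrollment through day 30".

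The Primary Analysis section of the SAP gives MAKE30 correlations from 11,582 patients in the year before the trial: 0.142 for ICU, 0.026 for month and below 0.001 for ICU by month. No correlations are given for fluid volumes, laboratory values or RRT indications.

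**The concern.** The SAP brings in a mixed model for the primary outcome because allocation is by ICU and month. Mann-Whitney and chi-square tests treat each hospitalization as independently allocated. Calendar-month effects do not cancel fully between arms, because three ICUs follow one sequence, two follow the other, and the ICUs start at different times. Where an ICU contributes unequal months to the two arms, ICU effects do not cancel either. A naive test can then call chance differences significant.

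Some of the affected rows carry weight. The SAP Discussion relies on reporting non-isotonic crystalloid, colloid and blood products to reveal treatment bias by unblinded clinicians; Table E3 carries the hypotonic crystalloid, albumin and blood product rows. Table E4 includes potassium above 5.0, which is safety-relevant because both balanced fluids contain potassium.

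**Working it through.** **Inputs.** From the documents: about 14,000 patients, MAKE30 about 15%, 82 unit-months, equal saline and balanced months per ICU, sequences split three ICUs to two, and the MAKE30 correlations above. Relative ICU volumes are taken either as equal or from Figure 12B of the 5/13/2015 protocol. Assumed: that the tested row resembles MAKE30 in its correlations and frequency, that the correlations are on the logit scale, and an equal-month schedule of 22 + 18 + 16 + 14 + 12 = 82.

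**The plan's own figure.** The Power Calculation says "Enrollment of 14,000 patients will provide 90% power at an alpha level of 0.05" for a 1.9% difference. With 7,000 per arm and rates of 15% and 13.1%, the null standard error is √(2 × 0.1405 × 0.8595 / 7,000) = 0.00587, as is the alternative one. Power = Φ((0.019 − 1.96 × 0.00587) / 0.00587) = 0.899. The figure is reproduced, treating patients as independent. Under independence the naive tests hold their size (simulated 5.0%).

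**Formula.** Let DE be the true variance of the naive difference divided by the variance the test assumes. Then the false-positive rate = 2 × [1 − Φ(1.96 / √DE)].

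**By hand, equal months per arm, correlations taken at face value:**
- ICU only: ICU effects cancel, but the naive variance still contains them. DE = 1 − 0.142 = 0.858, so the rate is 3.4%.
- ICU by month only, at the stated upper bound and 14,000 / 82 = 171 patients per unit-month: DE = 1 + 170 × 0.001 = 1.17, so 7.0%.
- ICU and month: month adds 0.948 (equal volumes) or 2.111 (Figure 12B volumes). DE = 1 − 0.142 + 0.948 = 1.806, so 14.5%; or 1 − 0.142 + 2.111 = 2.969, so 25.5%.

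Figure 12B volumes raise the rate because medical, surgical and trauma make up (2,300 + 2,126 + 1,693) / 9,223 = 66% of patients, against 60% with equal volumes, so month effects cancel less.

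**Logit scale.** Logit variances of 0.56 (ICU) and 0.103 (month) reproduce the stated values: with total 0.56 + 0.103 + 3.29 = 3.953, 0.56 / 3.953 = 0.142 and 0.103 / 3.953 = 0.026. At a 15% rate the proportion-scale correlations are about 0.56 × 0.15 × 0.85 = 0.071 and 0.103 × 0.1275 = 0.013, half the stated values. Halving all three correlations gives DE 1.488 to 2.073, so 10.8–17.3%. Null trials simulated on the logit scale, with a naive test of proportions, gave:

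| Schedule | ICU only | ICU and month |
|---|---|---|
| Equal months per arm in each ICU | about 4–5% | about 13–17% |
| Month counts read from Figure 1 | about 10–12% | about 17–23% |

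The ranges cover the schedule readings and, in most runs, both volume assumptions. One further equal-month run of 4,000 trials gave 17.9%, just above the range.

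**Month counts.** The stated dates, 1 June 2015 to 30 April 2017, give the medical ICU 7 + 12 + 4 = 23 months, which cannot split equally. If that ICU alone is unequal, ICU variation gives 5.9%. The higher ICU-only figures need odd counts in other ICUs as well. Those come from text-extracted figures that differ on when the trauma and surgical ICUs start.

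**Rarer rows.** On the equal-month schedule with ICU and month variation, a row at 2% gave 8.9% and a row at 0.5% gave 6.7%.

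**Table E5.** With 300–500 new-RRT patients (assumed), the formula gives 3.7–6.2%. Simulation with 400 patients and an assumed 30% indication prevalence gave 3.7–5.0%. The table leaves its denominator blank. With whole arms as denominator and 0.5–2% prevalence, the rate is 4.8–10.2%.

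**The case against.** The strongest reply is that the test-assignment sentence does not end at chi-square. It gives mixed models to secondary outcomes and GEE to repeated measures, and serum values are secondary outcomes, so Table E4 may already be covered. This stands in part, and it is why Table E4 is called ambiguous rather than wrong. It does not settle the matter. The E4 rows hold one value per patient (highest, lowest, or ever beyond a limit), so the repeated-measures clause fits poorly, and the column is not marked adjusted. The mixed model specified for the primary outcome also has a random effect for ICU only, so month would remain outside it. The R code that might resolve this is an additional file that is not among the documents.

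A second reply is that these analyses are hypothesis-generating and no decision rule uses them. That limits the consequence. It waives multiplicity correction but does not make a single P value valid.

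A reader might also infer that Tables E3 to E5 have a known error rate of 10–23%. The documents do not support that. The correlations are for MAKE30 alone, ignoring ICU does not inflate error when months are equal, and Table E5 has too few patients for material inflation when new-RRT patients are the denominator. In Table E3 the saline, lactated Ringer's, Plasma-Lyte and balanced rows differ by design, so no true null is at issue there.

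**Conclusion.** The point holds in a conditional form. For the hypotonic crystalloid, albumin and blood product rows of Table E3, the named tests ignore the design. For Table E4 the plan does not say clearly which test applies. Excess error under the equal-month design depends mainly on month variation. It reaches about 13–17% only if a full-cohort row has correlations and frequency like those of MAKE30, on a logit scale, and is lower for rarer rows. Unequal months, as read from Figure 1, would raise it to about 17–23%. Table E5 is not materially affected on new-RRT denominators. The documents give no correlations for these variables, so the size is an illustration and not an established rate. The primary analysis does not use these tests.

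**What to change.** State the test for each supplementary table. For Table E4 and the non-study-fluid rows of Table E3, take P values from models with ICU and calendar month: logistic for abnormal-value rows, and proportional-odds or linear for volumes and laboratory values. Where such a model does not fit, and for Table E5 and the study-fluid rows of Table E3, drop the P value or label it unadjusted and descriptive.

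The cost is modest. The modelled rows number 21 in Table E3 (three fluid categories of seven rows each) and 16 in Table E4, so 37 of the 77 rows in the three tables (53 + 16 + 8). The downside is extra model fitting for supplementary tables, with some volume rows likely to be zero-heavy and to need the descriptive fallback.
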